
Primary Objectives:

1. To explore whether receipt of IIV during the second week of the menstrual cycle (i.e., the week prior to ovulation) is associated with changes in steroid hormone levels, particularly decreases in progesterone, following ovulation.
2. To assess the feasibility of conducting further research in this area.

Primary Endpoints:

1. Changes in levels of estradiol and progesterone one week after receipt of influenza vaccination.

Exploratory Objectives:

1. To explore whether inflammatory cytokine responses to IIV receipt are associated with changes in reproductive hormone levels.
2. Identify optimal biomarkers of the inflammatory response after vaccination.
3. To collect peripheral blood mononuclear cells (PBMC) for future studies of cellular immune response.

Exploratory Endpoints:

1. Assess the inflammatory cytokine responses (including C-reactive protein [CRP]) to IIV.
2. To record adverse events in the 7 days after vaccination, including fever, myalgia, malaise, and hypersensitivity reactions.

II. Background and Rationale: Explain why this study is being done. Summarize briefly what is already known about the issue and reference previously published research, if relevant.

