1. Obtain blood for measurement of cytokines.

Day 17 +/-2 days (after ovulation), Day 21 +/- 2 days

Day 28 +/- 5 days (1st day of menstrual cycle)

1. Collect brief history of any new illnesses or problems since last visit
2. Review pregnancy prevention counseling.
3. Obtain blood for measurement of progesterone, and estradiol.

Day 21 +/- 2 days:

1. Collect approximately 30 cc of blood for PBMC processing.

Day 38-45

1. Participant to utilize LH strip at home, and call study staff when positive.
2. Participant to record on memory card results of LH strip.

Day 39 +/- 3 days (~ 11 days after menstruation; prior to ovulation)

1. Collect brief history of any new illnesses or problems since last visit
2. Review pregnancy prevention counseling.
3. Obtain blood for measurement of progesterone, estradiol, baseline cytokines and Hemagglutination Inhibition Assay (HAI).
4. Obtain approximately 30 cc of blood for PBMC processing.
5. Check urine pregnancy test.
6. Vaccinate subject with IIV.

Day 40 +/-1 day (1 day after vaccination), Day 41 +/-1 day (2 days after vaccination)

1. Collect brief history of any new illnesses or problems since last visit, ask about adverse events after vaccination.
2. Review pregnancy prevention counseling.
3. Obtain blood for measurement of cytokines.
Days 41-43 (2-4 days after vaccination).

Subject to answer questions reactivity in the REDCap database or on the memory card.

Day 45 +/-1 day (6-8 days after vaccination), Day 49 +/- 1 day (10-12 days after vaccination)

1. Collect brief history of any new illnesses or problems since last visit; ask about adverse events after vaccination.
2. Review pregnancy prevention counseling.
3. Obtain blood for measurement of progesterone, and estradiol.

Day 49 +/- 1 day (10-12 days after vaccination)

1. Obtain approximately 30 cc for PBMC processing.

Day 56 +/-4 days (1st day of menstruation)

1. Get brief history of any new illnesses or problems since last visit.
 2. Check urine pregnancy test.
 3. Obtain blood for measurement of progesterone, estradiol and for HAI.
3. Describe the expected duration of the study from the perspective of the individual participant and duration overall.

Each participant will spend about 3-4 months in the study, from screening to completion.
Each subject will be expected to come to approximately 14 visits

4. Provide a brief data analysis plan and a description of variables to be derived.

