The data will be analyzed using the computer software STATA (version 13, Stata Corp, College Station, TX). Each participant will serve as her own control. Summary data of the baseline characteristics of participants will be described using mean (SD) and median for continuous variables or frequencies and proportions for categorical data, as appropriate. Vaccine HAI titers will be measured prior to vaccination (day 39) and at 17 days following vaccination (day 56)

PA1: To determine if vaccination with IIV prior to ovulation (day 11 of menstruation) is associated with changes in post-ovulation serum reproductive (progesterone and estradiol) hormone concentrations.

-H 1: Post-vaccination serum reproductive hormone concentrations will be lower in the post-vaccination cycle than measured prior to vaccination.

The skewness of the hormone concentration distributions will be checked using Kolmogorov-Smirnov test or Shapiro-Wilks test. Transformation of the non-normal data to achieve normality will be attempted using natural logarithms or other mathematical functions. In the event that power transformations fail to normalize the data then non-parametric tests will be used. The mean difference (SD) between pre-vaccination serum hormone (progesterone and estradiol) concentrations and post-vaccination serum hormone concentrations measured during the luteal phase (days 17, 21, 28) of menstruation for each participant will be estimated using paired t-test for parametric data or by the Wilcoxon matched-pairs signed rank sum test for non-parametric data. A p-value < 0.05 will be considered statistically significant in all analyses. Stratified analyses will be conducted to determine if host characteristics modify the effects of vaccination on hormonal responses.

EA1: To determine if serum inflammatory biomarker (cytokines, chemokines, and C-reactive protein) concentrations differ following vaccination with IIV.

-H2: Serum pro-inflammatory biomarker concentrations at 24- and 48-hours post vaccination will be increased relative to baseline concentrations.

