The skewness of the cytokine concentration distributions will be checked using Kolmogorov-Smirnov test of normality. Transformation of the non-normal data to achieve normality will be attempted using natural logarithms. In the event that natural logarithm transformation fails to normalize the data then non-parametric tests will be used. Relationships between the different inflammatory biomarkers interest will be analyzed using Pearson's correlation or with Spearman's rank test, as needed. The mean difference (SD) in cytokine concentrations between baseline and at 24 hours post-vaccination, and between baseline and 48 hours post-vaccination within individuals will be evaluated by paired t-test for parametric data or by the Wilcoxon matched-pairs signed rank sum test for non-parametric data. Stratified analyses will be used to determine if host characteristics

modify the effects of vaccination on hormonal responses. Our study design will also allow us to look at differences in cytokines at various points in the nonvaccination menstrual cycle.

EA2: To determine if post-vaccination inflammatory biomarker responses to IIV receipt (days 40 and 41) are associated with changes in reproductive hormone levels during the second menstrual cycle.

-H3: Changes in serum pro-inflammatory responses between baseline and 24(and/or 48)-hours post-vaccination, will be inversely correlated with serum reproductive hormone concentrations during the second menstrual cycle.

Correlations between changes in post-vaccination serum pro-inflammatory biomarkers (days 39 to 40, 39 to 41) and changes in serum hormone responses during the second menstrual cycle (days 45 to 49, 45 to 56), will be calculated using Pearson's correlation coefficient and evaluated using the paired t-test for parametric data or Spearman's rank correlation test and the Wilcoxon matched-pairs signed rank sum test for non-parametric data. In addition, we will correlate changes in the hormone levels observed in the second cycle to the first cycle (days 17 to 21, 17 to 28) using the same analytical techniques.

EA4: To describe the frequency of adverse events in the 7 days after vaccination, including fever, myalgia, malaise, and hypersensitivity reactions, and to determine if these adverse events are associated with cytokines responses.

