-H4: Adverse events, specifically fever, myalgia and malaise after vaccination, are associated with a greater inflammatory cytokine response than seen in people who do not experience these events.

The frequency and proportion of participants who experience vaccine-associated adverse symptoms will be reported. In addition, differences in mean (SD) serum inflammatory biomarker concentrations at 24 and 48 post-vaccination and mean (SD) changes in serum concentrations following vaccination by adverse symptom status will be explored using t-tests.

5. **Answer the following if they are relevant to your study design:**

A. If the study has different arms, explain the process for assigning participants (intervention/control, case/control), including the sequence and timing of the assignment.

Subjects will be screened for eligibility based on their age, medical, vaccination and menstrual history, and birth control methods used. All participants will receive the same influenza vaccine. We will aim to enroll equal numbers of women who have received an H1N1 containing vaccine with influenza vaccine naïve women. This will allow us to compare responses of women with previous vaccination with those without prior history of vaccine.

B. If human biospecimens (blood, urine, saliva, etc.) will be collected, provide details about who will collect the specimen, the volume (ml) and frequency of collection, how the specimen will be used, stored, identified, and disposed of when the study is over. If specimens will be collected for use in future research (beyond this study), complete the "Biospecimen Repository" section below.

Specimens will be collected by the PI, nurses and staff trained in the proper collection of samples and blood draws. Serum specimens will be collected during this study. Any remaining specimens at the conclusion of the study will be retained under the CIR biorepository protocol (CIR 213 IRB Number R.22.05.04.29.A2.)

- C. If genetic/genomic analyses are planned, address whether the data will be contributed to a GWAS or other large dataset. Address returning unanticipated incidental genetic findings to study participants.

N/A

- D. If clinical or laboratory work will be performed at JHU/JHH, provide the JH Biosafety Registration Number.

N/A

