- H. Will you use clinical data of 500 records or more from Johns Hopkins Hospital and its affiliates?
Yes No

If yes, please complete the JHM Data Security Checklist available on the JHSPH IRB website:
www.jhsph.edu/irb and upload a copy of the checklist to the "Miscellaneous" section.

VII. Risks of the Study:

- A. Describe the risks, discomforts, and inconveniences associated with the study and its procedures, including physical, psychological, emotional, social, legal, or economic risks, and the risk of a breach of confidentiality. These risks should be described in the consent documents.

Risks to the participants are associated with the small risk that their personal information may be accidentally released. This is unlikely, as all reasonable effort will be made to restrict confidential information to those authorized to see it.

The inactivated influenza vaccine is routinely recommended by the ACIP for persons aged ≥ 6 months. The vaccine is generally well tolerated. The most common adverse events are fever, rash, injection site reactions, myalgia's and malaise. Rarely, there is a risk of allergic reaction, and in extremely rare circumstances, Guillain-Barré syndrome (1-2 additional cases per million people vaccinated). The risks of receiving the influenza vaccine while on study should not be any greater than the risk of receiving vaccine through routine preventative care, and are outlined in the CDC's Vaccine Information Sheet: <http://www.cdc.gov/vaccines/hcp/vis/index.htm>.

Phlebotomy: the main risk of phlebotomy is a bruise at the site of the needle insertion.

- B. Describe the anticipated frequency and severity of the harms associated with the risks identified above; for example, if you are performing “x” test/assessment, or dispensing “y” drug, how often do you expect an “anticipated” adverse reaction to occur in a study participant, and how severe do you expect that reaction to be?

We will be using the licensed inactivated influenza vaccine at the recommended dose. This vaccine has been used in millions of people each year, with well described adverse reactions. The most frequent adverse event related to influenza vaccination is pain at the injection site which can occur in up to 64% of people who receive the vaccine, and is usually mild and resolves within 2 days. Approximately 2% of subjects experience a myalgia/malaise syndrome that is also self-limited.

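### The reactogenicity questionnaire covers days 2-4 after vaccination while the adverse event endpoint covers 7 days, so symptoms are captured by different methods on different days.

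*Protocol*

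**What the plan says.** Exploratory endpoint 2 in the protocol is "To record adverse events in the 7 days after vaccination, including fever, myalgia, malaise, and hypersensitivity reactions". The data analysis plan repeats the window: "EA4: To describe the frequency of adverse events in the 7 days after vaccination". Its hypothesis H4 is that fever, myalgia and malaise "are associated with a greater inflammatory cytokine response than seen in people who do not experience these events". H4 is to be examined by t-tests of "differences in mean (SD) serum inflammatory biomarker concentrations at 24 and 48 post-vaccination" hours, and of changes after vaccination, by adverse symptom status.

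The visit list under Study Implementation places the self-report on "Days 41-43 (2-4 days after vaccination"), with the instruction "Subject to answer questions reactivity in the REDCap database or on the memory card". It states no look-back period.

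Three other provisions bear on the point:

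- At the Day 40, 41, 45 and 49 visits, staff take a history since the last visit and ask about adverse events.
- The Safety Monitoring section says volunteers are asked about reactions at each visit. Any reaction goes into the case report form with dates, duration, severity and relationship to vaccine.
- Section VII.D says participants are also asked to report adverse events in addition to attending visits.

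The SAP contains only the power calculation. It says nothing on adverse events.

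**The concern.** The structured instrument is shorter than the window it should serve. A form with set symptom questions, answered on the day, and a general question put by staff at a visit up to several days later are different measurements. A 7-day frequency that uses the form on some days and recall on the others mixes the two, and the plan does not say how to combine them.

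H4 depends on the same data. It splits women by symptom status, and neither document says whether that status comes from the form, the visit question, spontaneous reports or any of these. A woman with brief malaise on day 1 who does not mention it to staff would fall in the comparison group. A woman with the same symptom on day 3 would be asked about it on the form. Misplacing symptomatic women in this way pulls the cytokine difference toward zero.

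Fever adds a further question. It is a named event, but the schedule and visit list mention no temperature reading and no definition of fever. The form itself is not in the documents, so it may contain one.

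**Working it through.** **Time zero.** Vaccination is on study day 39: "Vaccine HAI titers will be measured prior to vaccination (day 39) and at 17 days following vaccination (day 56").

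**The plan's own figure.** 41 - 39 = 2 and 43 - 39 = 4, so the stated 2-4 days is reproduced.

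**Overlap with the endpoint.** Days 2, 3 and 4 are 3 of days 1-7, leaving days 1, 5, 6 and 7 without a questionnaire. Counting the vaccination day, they are 3 of 8, leaving days 0, 1, 5, 6 and 7.

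**What covers each day, at nominal visit times:**

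| Days after vaccination | Study days | Questionnaire | Visit question |
|---|---|---|---|
| 0-1 | 39-40 | No | Day 40, with the 24-hour cytokine sample |
| 2 | 41 | Yes | Day 41, with the 48-hour cytokine sample |
| 3-4 | 42-43 | Yes | By recall at Day 45 |
| 5-6 | 44-45 | No | Day 45 |
| 7 | 46 | No | By recall at Day 49, unless the Day 45 visit falls on day 7 or later |

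Every day is reached by some question. Only days 2-4 are reached by the questionnaire.

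**Visit windows counted from day 39.** Day 40 +/-1 gives days 0-2, Day 41 +/-1 gives days 1-3, Day 45 +/-1 gives days 5-7, and Day 49 +/-1 gives days 9-11. The protocol labels the last two visits 6-8 and 10-12 days after vaccination. The labels and the arithmetic differ by one day and should be reconciled. Under either reading, a Day 45 visit early in its window comes before day 7.

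**How many symptomatic women to expect.** Section VII.B of the protocol gives about 2% for a myalgia/malaise syndrome: 0.02 x 90 = 1.8 women. It gives no fever rate.

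**Illustration of the effect on H4.** The documents give no rate of missed symptoms, so this rests on an assumption. Let p be the true proportion with symptoms and m the fraction of them classed as symptom-free. Assume that missed women resemble those caught and that nobody is wrongly classed as symptomatic. The comparison group then contains a fraction pm / (1 - p + pm) of symptomatic women, and the mean difference shrinks by that fraction. With m = 0.5:

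- p = 0.02: 0.01 / 0.99 = about 1%.
- p = 0.30: 0.15 / 0.85 = about 18%.

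If symptoms are as rare as 2%, the harm is mainly the loss of one of about two cases. Bias matters only if symptoms are much commoner.

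**The case against.** The strongest reply is that the visits already cover the whole week. Staff ask about adverse events at Days 40, 41, 45 and 49, events are recorded with dates and severity, and participants may report between visits. That is correct, and it rules out three stronger readings that a reader might infer.

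- *Symptoms on days 0-1 are never solicited.* They are asked about directly at the Day 40 and 41 visits. Only the questionnaire is absent on those days.
- *The study misses the 24-hour cytokine time point.* The 24-hour sample and an adverse event question belong to the same Day 40 visit. The 48-hour point also lies inside the questionnaire window.
- *The questionnaire opens after the relevant symptoms have ended.* The statement in section VII.B that the reaction "is usually mild and resolves within 2 days" is about injection-site pain. H4 does not name pain, and the endpoint's list does not mention it. Myalgia and malaise are called self-limited, with no duration. The pain statement bears on H4 only indirectly.

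Two further points stand in part. The form's look-back is not stated, so a day-2 entry may ask about everything since vaccination. That would narrow the early gap to one of recall, but days 5-7 would still fall after the last entry. Also, if myalgia/malaise really occurs in about 2%, rarity limits H4 more than the questionnaire schedule does.

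None of this removes the difference in method between days, or supplies a rule for deriving symptom status.

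**Conclusion.** The point holds as a mismatch of method, not as missing data. A 3-day questionnaire serves a 7-day endpoint, and the remaining days depend on a general visit question and on participants' own reports. Symptom status for H4 is left undefined and could be assigned inconsistently.

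The conclusion rests on two readings: that the questionnaire is answered only on the days listed, and that its unstated look-back does not already reach day 0. If it does reach day 0, the gap on days 0-1 is one of recall and the main gap is days 5-7.

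The size of any under-count or attenuation cannot be computed from the documents; the 1% and 18% above are illustrations under a stated assumption. The reach is limited to exploratory endpoint 2, EA4 and H4. The primary comparison of progesterone and estradiol uses none of these data. This is an inexpensive improvement to an exploratory endpoint, not a defect in the main analysis.

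**What to change.** - Give the same REDCap or memory-card questionnaire daily from the evening of vaccination through day 7, that is Days 39-46. Define the window as days after the actual vaccination, so that it also works when the two cycles are exchanged (Day 39 then corresponds to Day 11, and Day 46 to Day 18).
- Include a self-recorded temperature, because fever is a named event, and state in advance what counts as fever.
- State the look-back period of each entry.
- Define H4 symptom status from this questionnaire, with the visit question as back-up where an entry is missing, and write the rule into the analysis plan.
- Reconcile the Day 45 and Day 49 labels with their windows.

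**Cost.** 8 - 3 = 5 more short entries per woman, with no added visit or staff. Participants are already trained on REDCap or the card at Day 0 and record LH strips on the card on Days 38-45, so home recording is extended by one day.

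**Drawback.** The 90 women include 30 from the pilot, whose symptom collection can no longer be changed, so at most 90 - 30 = 60 women could have the full form. Symptom data from the pilot women, and from anyone else followed before the change, should be reported separately or flagged, not pooled without comment.

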The power calculations are based on specific aim 1, with regards to changes in progesterone.

SA1: To determine if vaccination with IIV prior to ovulation (day 11 of menstruation) is associated with changes in post-ovulation serum reproductive (progesterone and estradiol) hormone concentrations.

-H 1: Post-vaccination serum progesterone concentrations will be lower in the month after vaccination than measured prior to vaccination.

We are planning to study 30 adult non-pregnant women each year. Based on the results from the first 30 student enrollees, we estimate the log (base 10) mean (SD) serum concentration of progesterone during the luteal phase of menstruation prior to vaccination is 0.71 (□ 0.51), and 0.58 (□ 0.54) post vaccination. This difference of -0.13 on the log (base 10) scale corresponds to a median ratio of 0.74 in other words, a 26% decrease in median progesterone levels after vaccination. The observed correlation in these log concentration values was 0.60. For a total sample size of 90 women (base task order and 2 option years), assuming similar standard deviation in log (base 10) pre- and post- vaccination values as observed in the initial sample of 30, the following table shows to the power to detect a given median post-vaccination to pre-vaccination concentration ratio for several pre- and post- concentration correlation values. These results are based on a type-1 error level of .05.

Median Ratio	Correlation		
	0.55	0.60	0.65
0.75	0.63*	0.69	0.74
0.70	0.82	0.86	0.90
0.65	0.93	0.95	0.97

* values in italics give estimated power to detect the specified median ratio for a specified correlation between the pre- and post-vaccination progesterone values

IV. Participants:

Describe the study participants and the population from which they will be drawn. Specify the inclusion and exclusion criteria. If you plan to include children, note their ages and whether you will include children in foster care. Note if the participants are particularly vulnerable in terms of cognitive limitations, education, legal migration status, incarceration, poverty, or some combination of factors.

Women aged 18-39 years will be recruited from Johns Hopkins University Campuses as well as from the surrounding community in East Baltimore. We will aim to include approximately equal numbers of women who have and have not previously received an H1N1-containing influenza vaccine.

A. Inclusion Criteria:

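### Normality checks on the hormone concentrations choose the scale and test of the primary analysis, so the plan does not fix the log-scale ratio for which power is stated

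*Protocol*

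**What the plan says.** **Analysis.** In the protocol, Section V, Study Implementation, item 4 (data analysis plan, aim PA1), the primary comparison starts with a distribution check: "The skewness of the hormone concentration distributions will be checked using Kolmogorov-Smirnov test or Shapiro-Wilks test". Non-normal data are to be transformed by natural logarithm or by some other function. Then: "In the event that power transformations fail to normalize the data then non-parametric tests will be used". The comparison of luteal values (days 17, 21 and 28) is by paired t-test or by Wilcoxon signed-rank test, depending on the outcome.

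The plan does not say:
- which of the two checks governs, or at what level;
- whether both cycles, both hormones and all days must share one transformation;
- on what scale the signed-rank differences are formed.

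**Power.** Protocol Section III.B and the SAP work wholly on the log10 scale, "assuming similar standard deviation in log (base 10) pre- and post- vaccination values" to those of the first 30 women. The effect is a ratio: "This difference of -0.13 on the log (base 10) scale corresponds to a median ratio of 0.74". No test is named. The SAP document contains only this power text, so it settles none of the open items.

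**The concern.** There are two faults of method.

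First, the check looks at the wrong quantity. A paired t-test rests on the distribution of the within-woman differences. Concentrations in each cycle can fail a normality test while their differences are well behaved, and the reverse.

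Second, the check decides what is estimated. A t-test on log differences estimates a ratio. A t-test after a square root, say, estimates a difference that has no simple reading. A signed-rank test gives no estimate unless one is specified, and its result depends on the scale on which the differences were formed. The choice could come out differently for progesterone and estradiol, or for day 17 and day 21. Only the log ratio matches the quantity for which power was stated.

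What is at stake is mainly how the result can be interpreted and whether the analysis is fixed in advance. The study is open label, so the analysis should be fixed in writing before the data can suggest it.

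**Working it through.** **Inputs (protocol Section III.B, repeated in the SAP).** 90 women; log10 SDs of 0.51 before and 0.54 after vaccination; "The observed correlation in these log concentration values was 0.60"; "These results are based on a type-1 error level of .05". Whether the test is one- or two-sided is not stated.

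**Assumptions not in the documents.** Log-normal data; one luteal value per woman per cycle; normality checks at the 0.05 level, applied to both cycles.

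**Step 1: reproduce the stated power.**
- SD of the log10 difference = √(0.51² + 0.54² − 2 × 0.60 × 0.51 × 0.54) = √0.2212 = 0.470.
- Effect at ratio 0.75 = log10(0.75) = −0.125.
- Noncentrality = 0.125 / 0.470 × √90 = 2.52.
- Two-sided paired t-test, 89 degrees of freedom: power 0.70 (stated 0.69).
- Ratios 0.70 and 0.65: 0.87 and 0.96 (stated 0.86 and 0.95).

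Across the nine cells of the table, eight agree within 2 points and the ninth is 2.2 points off (0.652 against 0.63). A one-sided test does not fit (0.81 against 0.69). The table therefore describes, in effect, a two-sided paired t-test on log differences.

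**Step 2: power of the log t-test and of the fallback on either scale** (simulation, 10,000 trials per cell, n = 90, correlation 0.60).

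| Test | Ratio 0.75 | Ratio 0.70 | Ratio 0.65 |
|---|---|---|---|
| Paired t, log differences | 0.70 | 0.87 | 0.96 |
| Signed-rank, log differences | 0.68 | 0.86 | 0.96 |
| Signed-rank, raw differences | 0.52 | 0.72 | 0.87 |

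Repeat simulations at ratio 0.75 gave 0.69 for signed-rank on log differences and 0.51 on raw differences. On the same data, the log t-test and the raw signed-rank test reach different significance verdicts in about 22% of trials. The two tests on log differences disagree in about 6%.

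**Step 3: how often the rank test is reached.** If log values are normal, a 0.05-level check on two cycles gives a false alarm in at most about 1 − 0.95² = 9.75% of trials. Simulation with Shapiro-Wilk gave 9.4% at ratio 0.75 and 9.7% at ratio 0.70. With Kolmogorov-Smirnov on standardised values, the log t-test was kept in over 99.9% of trials.

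**Step 4: average power of the whole rule** (Shapiro-Wilk; raw signed-rank as fallback; 5,000 trials).
- Ratio 0.75: 0.9058 × 0.711 + 0.0942 × 0.527 = 0.694, against 0.710 for always using the log t-test. Loss: 1.6 points.
- Ratio 0.70: 0.849 against 0.864. Loss: 1.5 points.

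Adding a short ladder of other power transformations before the fallback (exponents ±0.1 to ±0.5, assumed) cut the fallback rate to 2.4%. Power was then 0.712 against 0.716, a loss of 0.4 points.

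**Step 5: type I error when the rule is followed.** 0.048 without the ladder and 0.052 with it.

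**The case against.** The strongest reply is that little is lost. Average power falls by 2 points at most, type I error holds, natural log is the first transformation named (natural log and log10 give the same t-test), and the effect is already expressed as a log-scale ratio in the power section. The primary objective is worded as exploratory, and the protocol template asks only for a brief analysis plan. All of this stands, and it is why the point is minor. It does not supply a fixed scale, estimand or test.

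Four stronger readings are tempting, and the documents do not support them.

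- **A reader might infer that the plan risks a large loss of power.** The figure of about 0.51 needs log-normal data, a false alarm from the check and a signed-rank test on raw differences. The plan does not state that last condition. On log differences the loss is only 1 to 2 points.
- **A reader might infer that the raw signed-rank test is always the weaker choice.** If log values are truly non-normal, it need not be. With an assumed 20% of low-progesterone cycles it had 0.56 against 0.51 for the log t-test. In one assumed left-skewed mixture it had 0.80 against 0.71.
- **A reader might infer that the two checks will often disagree.** Under the planning inputs they lead to different tests in only about 10% of trials. Higher rates need an assumed share of low-progesterone cycles that the documents do not give.
- **A reader might infer an inflated false-positive rate.** An analyst who reported whichever of the log t-test and the raw signed-rank test was significant would reach about 7 to 8%. The plan describes a sequence, not that free choice.

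**Conclusion.** The point holds, at minor severity. The plan checks the distribution of the concentrations when the paired t-test depends on the differences, and it leaves the primary estimand and test to the outcome. Nothing in the power section or the SAP ties the analysis to the log-scale ratio.

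Under the planning inputs the expected loss of power is about 1.5 to 2 points or less. In the roughly 10% of trials or fewer that reach the fallback, the scale matters: about 0.51 for raw differences and about 0.69 for log differences, against about 0.70 for the log t-test. These figures rest on log-normal data and on the check level and single luteal value assumed above. The case for change does not depend on them. It rests on having one estimand, the same for both hormones and all days, that matches the power statement.

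**What to change.** In the data analysis plan, and repeated in the SAP:

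1. Name the two-sided paired t-test on within-woman log10 differences (vaccination cycle minus comparison cycle) as the primary analysis for both progesterone and estradiol, on every day analysed.
2. Report the back-transformed post/pre ratio with its 95% confidence interval.
3. Name the signed-rank test on the same log10 differences as the pre-stated sensitivity analysis.
4. Delete the normality check and the open choice of transformation.

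The cost is a few sentences. No visit, sample or sample size changes, and the stated power table then describes the analysis that will be run.
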